2. Presence of anatomical anomalies (e.g. solitary, horseshoe, fused crossed ectopia, pelvic kidney)
3. Presence of any prior urinary diversion (e.g. ileal conduit, orthotopic neobladder)
4. Presence of any indwelling ureteral stent prior to ureteroscopy
5. Presence of any indwelling nephrostomy tube prior to ureteroscopy
6. Ancillary ureteroscopy to treat residual fragments in the 3 months after percutaneous renal stone surgery.
7. Renal stone located in diverticulum
8. No indication for stent placement (e.g. spontaneous passage)
9. Bladder stone location
10. Pregnancy or lactation
11. Known allergic reactions to polyurethane or silicone

Section 7: SUBJECT SCREENING AND REGISTRATION PROCEDURES

Subjects will be recruited from predesignated MUSIC Urology clinics at participating institutions/sites.

Participating MUSIC Urologists will evaluate patients in their clinical practice for study inclusion or exclusion criteria. Preoperative evaluation, labs and imaging studies will be evaluated per the standard practice of the participating urologist based off best practice recommendations. It is the responsibility of the local site investigator/delegate to determine patient eligibility. If the urologist identifies their patient as a potential participant, the study will be discussed with them at their evaluation. The BLUES study brochure may also be given to the potential participant. If the subject expresses an interest, the urologist or local site delegate will contact the BLUES study team with the patient contact information and stone location (renal only or ureteral). The BLUES study team consists of the MUSIC ROCKS program manager, statistician, BLUES study coordinator(s), study principal investigator, and study co-investigator.

Enrollment in BLUES is voluntary. If a patient does agree to participate in BLUES, they will be enrolled prior to undergoing ureteroscopy and stent placement. The patient will undergo surgical consent for ureteroscopy and stenting per the routine clinical care process. Patients who agree to take part in the BLUES study will have their name, contact, and other clinical information relevant to their upcoming ureteroscopy and stent placement entered into the MUSIC registry.

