Participants at a given performance site who meet all inclusion/exclusion criteria will be randomized using Randomize.net or a similar randomization methodology as endorsed by the Michigan Institute for Clinical & Health Research (MICHR). Subjects will be randomized to either silicone or non-silicone ureteral stent placement at a 1:1 allocation ratio. Blocked, stratified randomization based upon surgeon classified stone location (renal only versus ureteral), with random block sizes will be used to ensure group balance. Randomization list will be determined separately in strata defined by state the stratification factor/s here. The randomization code will be generated by an independent statistician.

At the time of surgery, if baseline PRO has been completed, prior to placement of the stent, the surgeon will be notified via email/text message and the surgeons operating room staff can reference the MUSIC registry to confirm if the patient should have a silicone vs non-silicone stent based on random allocation by the BLUES study coordinator or another member of the BLUES study team. Only patients who are randomized, remain eligible prior to stent placement, and receive the study treatment will be counted towards the treatment population of 224 participants. These patients will receive PRO questionnaires, via the ROCKS PRO infrastructure, pre-operatively and at 7 days, and 4 weeks after surgery. If the patient is unable to complete the PRO questionnaires through the ROCKS PRO infrastructure, the patient may complete an email survey via REDCap, survey by phone from a BLUES study team member, or paper questionnaires. Patients will also receive text messages which include pain-specific questionnaires to be completed daily for 10 days after surgery. The process of completing the ROCKS PRO questionnaire is

the same, regardless of the patient's participation in the BLUES study. A patient can withdraw or decline participation in BLUES and/or ROCKS PRO at any time.

Section 8: TREATMENT PLAN

Section 8.1: Treatment overview

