An investigator may discontinue or withdraw a participant from the study for the following reasons:

- Significant study SoA non-compliance
 - No phone call, text message or email responses per SOA or study coordinator inquiries
- If any clinical adverse event (AE), laboratory abnormality, or other medical condition or situation occurs such that continued participation in the study would not be in the best interest of the participant
- If the participant meets an exclusion criterion (either newly developed or not previously recognized) that precludes further study participation
- Participant unable to receive phone calls, text messages or email for 5 of the 10 days postoperatively.

The reason for participant discontinuation or withdrawal from the study will be recorded on the Case Report Form (CRF) by the local study team member. Subjects who sign the informed consent form and are randomized but do not receive the study intervention may be replaced. Subjects who sign the informed consent form, and are randomized and receive the study intervention, and subsequently withdraw, or are withdrawn or discontinued from the study, will not be replaced.

Section 8.10: Patient Replacement

Subjects who sign the informed consent form, and are randomized and receive the study intervention, and subsequently withdraw, or are withdrawn or discontinued from the study, will not be replaced.

Subjects who are found to be ineligible at any time prior to ureteral stent placement may be replaced.

Section 9: STUDY PROCEDURES

Time and Events Table

Procedures	Baseline Evaluation	Prior to operation	Operative Day	Ambulatory Assessments Days 1-10	Ambulatory Assessment Day 7 ²	Postoperative visit: Stent removal	Ambulatory Assessment Week 4 ³	Day ≤ 30	Day ≤ 60
Informed consent		X							
Study education		X							
Demographics	X								
Medical history	X								
Randomization			X						
Study intervention				X					
Radiologic imaging assessment ¹	X								
Daily EMA				X					
ROCKS PRO		X			X		X		
Follow-up assessments of study endpoints and safety								X	X
Complete Case Report Form (CRF)			X			X		X	X

¹: Urological imaging modality performed nearest to but prior to operative date.

²: Day 7 ambulatory assessment can be completed from post-operative day 7 through day 10.

³: Week 4 ambulatory assessment can be completed from post-operative day 22 through day 42.

Section 10: ADVERSE EVENTS

Section 10.1: Adverse Event Reporting Requirements

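### The surgeon may learn the arm while eligibility is still open, so exclusions before stent placement can depend on the arm

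*Combined protocol and SAP*

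**What the plan says.** **Before randomization.** Section 6 requires all criteria to be met for enrollment. Section 7 asks for an eligibility worksheet signed by the site investigator or a designee, and randomizes only patients who meet every criterion. The time and events table in Section 9 puts randomization on the operative day.

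**Release of the arm.** Section 7 states that at surgery, "prior to placement of the stent, the surgeon will be notified via email/text message", and that operating room staff can use the registry to "confirm if the patient should have a silicone vs non-silicone stent based on random allocation". Section 10.4 describes blinding for patients only.

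**Eligibility after randomization.** Section 7: "Only patients who are randomized, remain eligible prior to stent placement, and receive the study treatment will be counted towards the treatment population" of 224. Section 8.10: "Subjects who are found to be ineligible at any time prior to ureteral stent placement may be replaced". Section 8.9: "Subjects who sign the informed consent form and are randomized but do not receive the study intervention may be replaced". Section 8.9 also lets an investigator withdraw a patient: "If the participant meets an exclusion criterion (either newly developed or not previously recognized) that precludes further study participation".

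**A criterion that can turn at surgery.** Section 6.2 excludes patients with "No indication for stent placement (e.g. spontaneous passage" given as the example.

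**Analysis sets.** In Section 11.3 the main efficacy set takes eligible, randomized participants who complete both pain questionnaires on days 7 to 10, analysed as assigned. The per-protocol set is also limited to eligible completers, and the safety set to patients who receive a stent. No set of all randomized patients is defined.

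**The concern.** Randomization makes the arms comparable only if who stays in the analysis does not depend on the arm. Here the person who makes the last eligibility decision may already know the arm, and a patient dropped at that step can disappear from the count and from every efficacy set. If surgeons were, even slightly, more ready to call a patient ineligible under one allocation than the other, the primary comparison would be between differently selected groups. Replacement would restore the number of patients and hence the power, but not the comparability. Random block sizes and an independent statistician protect concealment only up to the moment of release.

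**Working it through.** **Order of events.** Section 7 gives release a latest time (before stent placement) but no earliest time within surgery. Sections 7 and 8.10 give the final eligibility judgement the same latest time. No sentence puts one before the other, so the plan permits release first and exclusion second.

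**Is there room for judgement?** Section 4.2 reports that stent use after ureteroscopy varies between surgeons from 10% to 100%. In Appendix 1, for patients without a prior stent, with stones up to 5 mm and no basketable fragments left, the panel rated stent omission 9 without an access sheath and 3 with one. The trial excludes patients with an indwelling stent and sets no minimum stone size. So the need for a stent can turn on what happens during the operation.

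**The plan's own figure.** Section 11.2 assumes a difference of 5, SD 10 and two-sided alpha 0.025. The noncentral t distribution gives 90.1% power at 101 per arm and 89.8% at 100, so 101 is reproduced. Allowing for 10% loss, 202 / 0.9 = 224.4, against the stated 224. Nothing here challenges the sample size.

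**Illustrative bias.** The documents give neither an exclusion rate nor the prognosis of excluded patients, so both are assumed. Let a fraction q of one arm only be dropped, with a mean day-7 T-score that differs by s from the mean m of the full arm. If r is the mean of those retained:

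m = (1 − q)r + q(m + s), so r = m − qs/(1 − q), and the bias is b = qs/(1 − q).

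The standard error of the difference is 10 × √(2/101) = 1.407, and the critical value for two-sided 0.025 is 2.241. With Φ the standard normal distribution function, the type I error is Φ(−2.241 + b/1.407) + Φ(−2.241 − b/1.407).

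| q (one arm only) | s | b (points) | Type I error per endpoint |
|---|---|---|---|
| 2% | 5 | 0.10 | 2.5% |
| 2% | 10 | 0.20 | 2.7% |
| 5% | 5 | 0.26 | 2.8% |
| 5% | 10 | 0.53 | 3.5% |
| 10% | 5 | 0.56 | 3.7% |
| 10% | 10 | 1.11 | 7.4% |

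The test is two-sided, so the sign of s does not change the error rate. If both arms lose the same fraction with the same s, the two shifts cancel and b = 0. The table ignores baseline adjustment, in line with the zero baseline correlation that Section 11.2 assumes.

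**The case against.** The plan has real protections, and several stronger readings that a reader might take from it fail.

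- *That the surgeon never commits to eligibility before seeing the arm.* Not so. The worksheet and the all-criteria check come before randomization. What is missing is a second commitment for the period that Sections 7 and 8.10 reopen.
- *That dropped patients are always replaced.* The text only permits replacement, and replacement creates no bias in itself.
- *That leaving the count of 224 means leaving the analysis.* The count is an accrual rule. The modified intention-to-treat set does not require a stent, and a patient who receives the other stent type stays in the assigned arm. Section 11.3 does not say at what time a participant must be eligible. Eligibility up to placement is the natural reading, given Sections 7 and 8.10, but it is a reading.
- *That the analysis can do nothing.* The ANCOVA removes the part of any selection that runs through baseline pain. It cannot remove the rest.
- *That arm-dependent exclusion will happen.* Nothing shows this. The example attached to the criterion, spontaneous passage, is a matter of fact rather than a preference between materials, and both arms use approved stents in the same listed sizes.

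It is also fair to say that release at the end of ureteroscopy would already fit Section 7, since Section 8.2 places the stent at the end of the procedure. The Section 1 schema and the Figure 3 flow chart were not visible in the text available to me and may show the order. These points limit the size and likelihood of the problem. They do not close the gap, because the written rules still allow exclusion by someone who knows the arm.

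**Conclusion.** The point holds as a gap in the written rules. Eligibility stays open until stent placement, the arm may be known before then, and no defined efficacy set clearly recovers patients dropped in between. The size is unknown. With 2% to 10% dropped from one arm only and a gap of 5 to 10 points, the bias is about 0.1 to 1.1 T-score points, or 2% to 22% of the 5-point design difference, and the type I error per endpoint is about 2.5% to 7.4%. At the low end this is negligible. The high end needs both a one-sided 10% loss and a gap of a full SD. The documents support neither as an expectation, nor any claim that exclusions will in fact differ by arm. The plan should still be changed, because the remedy costs little and the bias could not be fully repaired afterwards.

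**What to change.** - **Section 7:** release the allocation, both the message and the registry display, only after the surgeon has recorded that the patient remains eligible and that a stent will be placed. Exclusions before that record then cannot depend on the arm, and those patients may be replaced.
- **Sections 8.9, 8.10 and 11.3:** count everyone whose allocation has been released, do not replace them, and analyse them in the assigned arm. Define eligibility for the modified intention-to-treat set as status before release. Keep sending these patients the questionnaires. Section 7 ties these to the counted patients, although it says the ROCKS PRO process is the same whether or not a patient takes part in BLUES.
- **Reporting:** list any exclusion after release by arm, with the reason.

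The sample size does not change, and the fix fits the operative-day randomization in Section 9. The cost is a brief record during surgery, near-real-time release at six practices, and having both stent types at hand.

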Participating BLUES practices will utilize the MUSIC Registry and ROCKS PRO as a tool to enroll and collect patient surveys. Through ROCKS PRO, patients are provided via email a secure and unique link to the MUSIC Registry patient portal. An electronic introduction for ROCKS PRO will then be presented. Patients will not be required to participate and may choose to be removed from future correspondence by emailing or calling the MUSIC Coordinating Center directly.

If participating, they will be directed to the baseline questionnaire consisting of questions regarding health-related symptoms, functions and pain management before undergoing ureteroscopy. Automated email survey links will be sent to patients to complete ROCKS PRO questionnaires pre-operatively and at 7 days, and 4 weeks after surgery (Figure 1). Patients with cell phone numbers who agree to participate in BLUES will be asked to complete EMA of pain via a visual analog scale score and one question from the PROMIS® Ability to Participate in Social Roles and Activities Questionnaire (Figure 2), for 10 days after surgery.

If a patient does not log-in or fails to complete the baseline survey, they will receive an electronic automated reminder and will be contacted by the MUSIC Coordinating Center. If a patient does not log-in or fails to complete the 7-day survey, they will receive an electronic automated reminder and will be contacted by the MUSIC Coordinating Center on day 8 and 9, to facilitate its completion by the end of post-operative day 10. The BLUES Study Team may also administer the PRO questionnaires via REDCap, phone, or paper if the participant is unable to complete surveys through the MUSIC Registry.

Figure 3 depicts the timeline and flow chart of the recruitment and follow-up process. If it is past the patient's operative date they will not be enrolled or contacted.

The patient's surgery will proceed per standard of care, and their follow up, imaging and clinic visits will be directed by the local surgeon according to their local protocol. The BLUES study is pragmatic. Stents will be removed at a time and duration per the surgeon's discretion. The patient's information regarding post-operative course will be collected into the registry 60 days after the surgery, keeping with current practice for MUSIC ROCKS patient registry entry.

Section 8.2: Operative

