An adverse event (AE) is considered "unexpected" if it meets the criteria of an AE per section 10.2, and is not expected as described above.

Section 10.3: Reporting of Unanticipated Problems

Upon becoming aware of any incident, experience, or outcome (not related to an adverse event) that may represent an unanticipated problem, the investigator should assess whether the incident, experience, or outcome represents an unanticipated problem. The incident, experience or outcomes is considered unanticipated if it meets all of the following criteria:

1. Unexpected (in terms of nature, severity, or frequency);
2. Related or possibly related to participation in the research; and
3. Suggests that the research places subjects or others at a greater risk of harm than was previously known or recognized.

If the investigator determines that the incident, experience, or outcome represents an unanticipated problem, the investigator must report it to the IRB according to the local IRB policies.

Section 10.4: Unblinding Procedures

To minimize bias in patient-reported outcome measures, all reasonable efforts will be made to keep patients blinded to their randomized treatment allocation. This will help to assure that all patient-reported outcomes and clinical data collection for the trial have been completed prior to unblinding. Patients will be notified of their randomized treatment allocation by trial staff at the coordinating center at the conclusion of the study.

In the case of a medical emergency or other event in which the participant's knowledge of their treatment allocation is critical to the participant's clinical management, the blinding for that participant may be broken by the investigator. The investigator or their designee must document the date and reasons for such emergency unblinding in the participant's source documents. The investigator must also immediately notify the study PI and trial coordinating center of such an event.

Section 10.5: Stopping Rules

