These 6-month meetings are to be documented by the BLUES study coordinator or the BLUES trial project manager and will include the topics listed above as appropriate. The meeting minutes must be signed by the Principal Investigator or by one of the co-investigators.

The BLUES study team is responsible for collating all the meeting documentation for participating sites and will report any serious adverse events, unanticipated problems, and protocol deviations as outlined in section 10.

Section 13: QUALITY ASSURANCE AND AUDITS

The Data and Safety Monitoring Committee can request a 'for cause' quality assurance audit of the study if the committee identifies a need for a more rigorous evaluation of study-related issues.

A regulatory authority (e.g. FDA) may also wish to conduct an inspection of the study, during its conduct or even after its completion. If an inspection has been requested by a regulatory authority, the site investigator must immediately inform the BLUES study team that such a request has been made.

Section 14: CLINICAL MONITORING PROCEDURES

Prior to subject recruitment, a participating site will undergo site initiation meeting to be conducted by the BLUES study team. This will be done as a teleconference, videoconference, or web-based meeting after the site has been given access to the study database, provided the BLUES study team the necessary regulatory documentation and received IRB approval. The site's principal investigator and study staff should make every effort in attending the site initiation meeting. Study-related questions or issues identified during the site initiation meeting will be followed-up by the appropriate BLUES study team personnel until they have been answered and resolved.

Monitoring of this study will include centralized surveillance of study specific MUSIC registry data by the BLUES study team to confirm adherence to the protocol. The BLUES study team will meet at least once per month to review findings of surveillance and may engage sites ad-hoc as appropriate. Additional monitoring will be performed by the BLUES study staff members on an annual basis.

REFERENCES

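### The fallback phone route for the day-7 pain questionnaires allows a caller who knows the arm, because the same central team handles allocation and only patients are blinded.

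*Combined protocol and SAP*

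**What the plan says.** **Collection of the primary endpoints.** Under Section 8.1 the default is an emailed link that the patient completes alone. For patients who cannot use that route, Section 7 lists an emailed REDCap survey, a "survey by phone from a BLUES study team member", or a paper form. Section 8.1 restates this: "The BLUES Study Team may also administer the PRO questionnaires via REDCap, phone, or paper if the participant is unable to complete surveys" through the registry. The questionnaires include the PROMIS pain items, whose day-7 T-scores are the two primary endpoints (Section 11.4).

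**Who handles allocation.** Section 7 says that the surgeon is notified, and operating room staff can check the registry, "based on random allocation by the BLUES study coordinator or another member of the BLUES study team". The list itself is prepared elsewhere: "The randomization code will be generated by an independent statistician".

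**Who the team is.** Section 7: "The BLUES study team consists of the MUSIC ROCKS program manager, statistician, BLUES study coordinator(s), study principal investigator, and study co-investigator". No split into blinded and unblinded members is described.

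**What the team can see.** Section 14 provides for "centralized surveillance of study specific MUSIC registry data by the BLUES study team". Under Section 8.2, the size, brand and name of the stent placed are collected through the ROCKS clinical registry.

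**Who is blinded.** Section 10.4 says that "all reasonable efforts will be made to keep patients blinded to their randomized treatment allocation". It gives the reason as limiting bias in the patient-reported outcomes. It says nothing about those who administer the questionnaires.

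**The concern.** Both primary endpoints are subjective pain reports, and the trial's hypothesis is that silicone is superior. When a person reads the items aloud, the answer can be affected by how an item is rephrased, by a follow-up prompt, or by how a hesitant reply is entered. A caller who knows the arm may also let it slip to a patient who is meant not to know it. If the caller shares the trial's expectation, these influences would tend to favour silicone on both endpoints.

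Section 10.4 protects the patient's blinding for this very reason, but the phone route leaves the other end of the line open. The documents do not require the caller to be unaware of the arm, give a call script, or provide for recording how each questionnaire was completed. Without a record of mode, nobody could check afterwards whether phone use differed by arm or whether the result depends on phone-collected scores.

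**Working it through.** **1. Does the text permit a caller who knows the arm?**
- Section 7 and Section 8.1 allow phone administration by a member of the study team, with no further condition on which member.
- Section 7 places allocation with the coordinator or another member of that team.
- Section 14 gives the team registry data to review, and Section 8.2 puts the stent's brand and name in the registry. A member who did not handle the allocation could still see the arm.
- Section 10.4 covers patients only. The independent statistician in Section 7 protects generation of the sequence, not knowledge of individual assignments once they are released.

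Together these permit it. They do not say that it will happen, or that one individual does both tasks.

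**2. The plan's own figure.** Section 11.2 uses a difference of 5 points, SD 10, two-sided alpha 0.025 and 101 patients per arm for 90% power.
- Standard error of the arm difference: 10 × √(2/101) = 1.407.
- Exact two-sample t-test: required n = 100.6, so 101 per arm; power at 101 is 0.901. The stated figure reproduces.

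**3. How much could phone administration matter?** The documents give neither the phone share nor any size for an interviewer effect. Both are assumptions here:
- share of day-7 scores collected by phone, f: 10%, 20% or 30%, equal in the two arms (about 10, 20 or 30 of 101 patients per arm);
- between-arm shift among phone-collected scores caused by the caller, b: 2, 3 or 5 points.

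Shift in the overall arm difference = f × b. With no true effect, the rejection probability comes from the noncentral t distribution with 200 degrees of freedom and noncentrality (f × b)/1.407, at two-sided alpha 0.025. As in Section 11.2, the correlation with baseline is set to 0.

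| f | b (points) | Shift f × b | Noncentrality | Per-endpoint type I error |
|---|---|---|---|---|
| none | – | 0 | 0 | 2.5% |
| 10% | 2 | 0.2 | 0.14 | 2.6% |
| 20% | 3 | 0.6 | 0.43 | 3.8% |
| 20% | 5 | 1.0 | 0.71 | 6.4% |
| 30% | 5 | 1.5 | 1.07 | 11.9% |

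A shift against silicone would cost power instead. At a true difference of 5 points, power falls from 90% to 87% with a shift of 0.2 points, 81% with 0.6 and 59% with 1.5.

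**The case against.** The strongest reply is that the exposed group may be small and the mechanism weak. Phone is a fallback for patients unable to use the registry, and the two other fallback routes, REDCap and paper, are self-completed. The items have fixed wording and five fixed response options (Figure 1). The answers come from patients who are meant to be blinded, and the caller rates nothing. The upper assumed shift of 5 points equals the whole difference that the trial is powered to detect, and 11.9% needs that shift together with the highest phone share. Section 4.4 also mentions a manual of operation, which may contain scripts and task assignments. Most of this stands. It limits the likely size, but it does not supply the missing safeguard in the protocol.

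A reader might infer more than the documents support:
- *That late responders are the ones interviewed by phone.* Section 8.1 describes Coordinating Center contact on days 8 and 9 to prompt completion. It does not say that the contact is by phone or that the questionnaire is administered then. The phone survey is for patients who are unable, which is not the same as late.
- *That a site coordinator passes on the arm and then phones the patient.* The phone survey belongs to the central team as Section 7 defines it. Local site designees are named separately.
- *That the endpoint is assessed by unblinded raters.* It remains patient-reported.
- *That disclosure to the patient is wholly unaddressed.* Section 10.4 partly covers it through the commitment to keep patients blinded.

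**Conclusion.** The point holds as a gap in safeguards. For patients who cannot complete the survey online, the plan allows both primary endpoints to be collected in conversation with a central team member who may know the arm, and nothing requires otherwise. This rests on the text and is firm.

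The size is unknown. The range of 2.6% to 11.9% per endpoint follows entirely from an assumed phone share of 10–30% and an assumed shift of 2–5 points. The effect is negligible at the low end, and becomes material only if phone use is common and the caller's influence amounts to several points. The documents do not support reading 11.9% as an expected error rate, or concluding that the trial will be biased. The change is still worth making, because the endpoint is subjective and the remedy is cheap. Without a record of mode, the question could not be settled later. The sample size need not change.

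**What to change.** In Sections 7 and 8.1:

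1. Offer the self-completed fallbacks (REDCap email or paper) before phone.
2. Allow phone administration only by existing staff who did not handle that patient's allocation and who do not view that patient's allocation or stent fields. Coordinating Center staff qualify only on the same terms: the centre maintains the registry (Section 6), and its trial staff tell patients their arm at the end of the study (Section 10.4).
3. Use a fixed call script that does not mention stent type.
4. Record the mode of administration for every questionnaire.

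In Section 11.4, report mode by arm and add a sensitivity analysis of both primary endpoints that excludes phone-collected scores. Because mode is determined after randomization, this analysis should support the main one and not replace it.

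The cost is less flexibility over who calls, and either a registry access restriction or a split of tasks within the team. The documents do not say whether the registry can hide fields. If it cannot, the task split has to do the work, together with a rule that callers do not open those fields. Endpoints, sample size and clinical care stay as they are.
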